### **7.4.1. Prior Medications**

Prior medications are defined as any medication taken before a subject took the first study drug.

Prior medications will be summarized by Anatomical Therapeutic Chemical (ATC) drug class preferred name using the number and percentage of subjects for each treatment group and overall. A subject reporting the same medication more than once will be counted only once when calculating the number and percentage of subjects who received that medication. The summary will be provided by preferred name in order of descending overall frequency. For drugs with the same frequency, sorting will be done alphabetically.

For the purposes of analysis, any medication with a start date prior to the first dosing date of any study drug will be included in the prior medication summary regardless of when the stop date is. If a partial start date is entered the medication will be considered prior unless the month and year (if day is missing) or year (if day and month are missing) of the start date are after the first dosing date. Medications with a completely missing start date will be included in the prior medication summary, unless otherwise specified.

Summaries will be based on the Safety Analysis Set. No formal statistical testing is planned.

### **7.4.2. Concomitant Medications**

Concomitant medications are defined as medications taken while a subject took study drug. Use of concomitant medications will be summarized by ATC drug class preferred name using the number and percentage of subjects for each treatment group. A subject reporting the same medication more than once will be counted only once when calculating the number and percentage of subjects who received that medication. The summary will be provided by preferred term in descending overall frequency within each ATC medical class. For drugs with the same frequency, sorting will be done alphabetically.

For the purposes of analysis, any medication with a start date prior to or on the first dosing date of any study drug and continued to take after the first dosing date, or started after the first dosing date but prior to or on the last dosing date of study drug will be considered concomitant medications. Medications started and stopped on the same day as the first dosing date or the last dosing date of any study drug will also be considered concomitant. Medications stopped on the same day as the first dosing date will be considered concomitant. Medications with a stop date prior to the date of first dosing date of any study drug or a start date after the last dosing date of any study drug will be excluded from the concomitant medication summary. If a partial stop date is entered, any medication with the month and year (if day is missing) or year (if day and month

are missing) prior to the date of first study drug administration will be excluded from the concomitant medication summary. If a partial start date is entered, any medication with the month and year (if day is missing) or year (if day and month are missing) after the study drug stop date will be excluded from the concomitant medication summary. Medications with completely missing start and stop dates will be included in the concomitant medication summary, unless otherwise specified.

Summaries will be based on the Safety Analysis Set. No formal statistical testing is planned.

All prior and concomitant medications (other than per-protocol study drugs) will be provided in a by-subject listing sorted by subject ID number and administration date in chronological order.

## **7.5. Electrocardiogram Results**

### **7.5.1. Investigator Electrocardiogram Assessment**

A shift table of the investigators' assessment of ECG results at each visit compared with baseline values will be presented by treatment group using the following categories: normal; abnormal (not clinically significant); abnormal (clinically significant); or missing. The number and percentage of subjects in each cross-classification group of the shift table will be presented. Subjects with a missing value at baseline or postbaseline will not be included in the denominator for percentage calculation.

No formal statistical testing is planned.

A by-subject listing for ECG assessment results will be provided by subject ID number and visit in chronological order.

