On-treatment assessments will include: adverse events (AEs), concomitant medications, review of study medication compliance through drug accountability, SJC66, TJC68, Subject's Global Assessment, Subject's Pain Assessment, HAQ-DI, Functional Assessment of Chronic Illness Therapy-Fatigue (FACIT-Fatigue), Short-Form Health Survey (SF-36), Work Productivity and Activity Impairment- Rheumatoid Arthritis (WPAI-RA), EuroQol 5 Dimensions (EQ-5D), CCI [REDACTED] Treatment Satisfaction Questionnaire for Medication (TSQM), Healthcare Resource Utilization, Physician's Global Assessment, physical examination, weight, vital signs, serum CRP, blood and urine sampling for safety laboratory tests and biomarkers at selected visits, and urine pregnancy tests (females of child bearing potential only).

A resting 12-lead ECG should be performed at Screening, Weeks 12, 24, 36, and 52 or ET, and at the Post-treatment Week 4 follow-up visit. ECGs should be interpreted by the investigator (or qualified designee) for clinical significance.

For all subjects, blood samples for PK analysis should be collected at least 30 minutes post study drug dose on Week 4, prior to study drug administration on Weeks 12 and 24, and any time at the final assessment visit on Week 52 or ET.

CCI [REDACTED]

Blood samples for biomarker analysis should be collected at Day 1, Weeks 4, 8, 12, 24, 36, and Week 52 or ET and urine samples should be collected at Day 1, Weeks 12, 24, and Week 52 or ET.

Radiographs of the bilateral hands, wrists, and feet should be taken at Screening, Week 24, and Week 52 or ET. However, if a subject prematurely discontinues study participation and has had X-rays performed within the previous 12 weeks, then X-rays do not need to be repeated at the ET visit. Radiographs performed after enrollment may be done +/-7 days of the scheduled visit.

Post treatment follow-up assessments include AEs, concomitant medications, physical examination, 12-lead ECG, weight, vital signs, blood and urine sampling for safety laboratory tests, and urine pregnancy tests (females of child bearing potential only).

CCI

[REDACTED]

Test Product, Dose, and Mode of Administration:	200 mg filgotinib orally q.d. plus MTX weekly up to 20 mg 100 mg filgotinib orally q.d. plus MTX weekly up to 20 mg 200 mg filgotinib orally q.d.
--	---

Reference Therapy, Dose, and Mode of Administration:	MTX weekly up to 20 mg or PTM MTX weekly PTM filgotinib 200 mg orally q.d. PTM filgotinib 100 mg orally q.d.
---	--

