**Table 3-2. Analysis Visit Windows for On-Treatment ECG Data**

Analysis Visit	Nominal Study Day	Lower Limit	Upper Limit
Baseline	1	(none)	1
Week 12	85	2	127
Week 24	169	128	211
Week 36	253	212	309
Week 52	365	310	≥ 365

The analysis windows for on-treatment lipid data are provided in [Table 3-3](#).

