### 3.8.3. Selection of Non-Efficacy Data in the Event of Multiple Records in an Analysis Visit Window

Depending on the statistical analysis method, single values may be required for each analysis window. For example, change from baseline by visit usually requires a single value, whereas a time-to-event analysis would not require 1 value per analysis window.

If multiple valid, nonmissing, continuous measurements exist in an analysis window, records will be chosen based on the following rules if a single value is needed:

- In general, the baseline value will be the last nonmissing value on or prior to the first dosing date of study drug, unless specified differently. If multiple measurements occur on the same day, the last nonmissing value prior to the time of first dosing of study drug will be considered as the baseline value. If these multiple measurements occur at the same time or the time is not available, the average of these measurements (for continuous data) will be considered the baseline value.
- For postbaseline visits:
  - The record closest to the nominal day for that visit will be selected.
  - If there are 2 records that are equidistant from the nominal day, the later record will be selected.
  - If there is more than 1 record on the selected day, the average will be taken, unless otherwise specified.

If multiple valid, nonmissing, categorical measurements exist in an analysis window, records will be chosen based on the following rules if a single value is needed:

- For baseline, the last available record on or prior to the date of the first dose of study drug will be selected. If there are multiple records with the same time or no time recorded on the same day, the value with the lowest severity will be selected (eg, normal will be selected over abnormal for safety ECG findings).
- For postbaseline visits:
  - The record closest to the nominal day for that visit will be selected.
  - If there are 2 records that are equidistant from the nominal day, the later record will be selected.
  - If there is more than 1 record on the selected day, the value with the worst severity will be selected (eg, abnormal will be selected over normal for safety ECG findings), unless otherwise specified.

The rules for selecting efficacy data in the event of multiple records in an analysis visit window are specified in Section [6.1](#).

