### **7.2.2.3. Summaries of Laboratory Abnormalities**

Laboratory data that are categorical will be summarized using the number and percentage of subjects in the study with the given response at baseline and each scheduled postbaseline visit.

The following summaries (number and percentage of subjects) for treatment-emergent laboratory abnormalities will be provided by laboratory test and treatment group; subjects will be categorized according to the most severe postbaseline abnormality grade for a given laboratory test:

- Graded laboratory abnormalities

- Grade 3 or higher laboratory abnormalities
- Marked laboratory abnormalities

For all summaries of laboratory abnormalities, the denominator is the number of subjects with nonmissing postbaseline values up to 30 days after last dosing date.

A by-subject listing of treatment-emergent Grade 3 or higher laboratory abnormalities and marked laboratory abnormalities will be provided separately by subject ID number and visit in chronological order. These listings will include all test results that were collected throughout the study for the laboratory test of interest, with all applicable severity grades or abnormal flags displayed.

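### The only planned ECG table is by visit and keeps one ECG per wide window, so some on-treatment early-termination and unscheduled ECGs reach no ECG table

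*SAP*

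**What the plan says.** **Schedule.** The Protocol Synopsis states: "A resting 12-lead ECG should be performed at Screening, Weeks 12, 24, 36, and 52 or ET". It adds one more at the Post Treatment Week 4 visit.

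**Summary.** In SAP 7.5.1 the investigators' "assessment of ECG results at each visit compared with baseline values will be presented by treatment group", in three categories (normal, abnormal but not clinically significant, abnormal and clinically significant) plus missing. A chronological by-subject listing goes with it. SAP 7.5 has no worst-value or any-time ECG summary and no QTcF summary, although Protocol 6.7.6.1 says QTcF will be derived at analysis. The shift table is therefore the only by-arm ECG display.

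**Windows.** SAP Table 3-2 sets Days 2-127 for Week 12, 128-211 for Week 24, 212-309 for Week 36 and 310 onward for Week 52. The nominal days are 85, 169, 253 and 365.

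**Selection.** For categorical data, SAP 3.8.3 says "records will be chosen based on the following rules if a single value is needed". For postbaseline visits: "The record closest to the nominal day for that visit will be selected". Of two equidistant records the later is kept. Severity enters only at the last step: "If there is more than 1 record on the selected day, the value with the worst severity will be selected". It breaks ties within the selected day and does not search the window. SAP 7.5.1 does not cite 3.8.3, but 3.8.3 uses safety ECG findings as its own example, so the rule covers this table.

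**Limits in time.** SAP 3.8.2 applies these windows up to last dose + 7 days. ECGs from + 8 to + 30 days are summarized separately, keeping the latest record. Anything later is listed only.

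**Laboratory comparison.** In SAP 7.2.2.3, "subjects will be categorized according to the most severe postbaseline abnormality grade for a given laboratory test". SAP 7.2.3.1 (liver) and 7.2.3.2 (blood counts) also work from the worst postbaseline result.

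**The concern.** An ECG taken when a subject leaves the study, or outside the schedule, is among those most worth seeing by arm. Suppose a subject has a normal scheduled ECG on Day 85 and an abnormal, clinically significant ET ECG on Day 110, still within 7 days of last dose. Both fall in the Week 12 window, Day 85 is nearer nominal, and the table shows normal to normal. The Day 110 result is in the listing, but no ECG table counts it.

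At stake is the by-arm picture of ECG changes that are clinically significant but asymptomatic, or that resolve before follow-up. Such changes have no assured route into another summary.

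**Working it through.** **The plan's own figures.** The Table 3-2 limits are the midpoints of adjacent nominal days: (85 + 169)/2 = 127, (169 + 253)/2 = 211, (253 + 365)/2 = 309. All three match.

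**Assumptions** (the documents give no exit timing): scheduled ECGs on the nominal day, ET ECG within 7 days of last dose, no unscheduled ECG, exits spread evenly over days.

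**Rule.** An ET ECG is displaced if an earlier scheduled ECG in the same window lies strictly nearer the nominal day. With scheduled ECGs on the nominal day, that is every ET day after nominal and up to the window's upper limit.

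| Window | Days | Nominal day | ET ECG displaced on | Number of days |
|---|---|---|---|---|
| Week 12 | 2-127 | 85 | 86-127 | 42 |
| Week 24 | 128-211 | 169 | 170-211 | 42 |
| Week 36 | 212-309 | 253 | 254-309 | 56 |
| Week 52 | 310 onward | 365 | none up to Day 364 | 0 |

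- Exits on Days 86-364: 364 - 86 + 1 = 279 days. Displaced: 42 + 42 + 56 = 140. Share: 140/279 = 50%.
- Scheduled ECGs 3 days off nominal: an ET ECG at most 3 days from nominal is kept (a tie goes to the later record), so displacement starts 4 days after nominal. Days 89-127, 173-211 and 257-309 give 39 + 39 + 53 = 131, and 131/279 = 47%.
- Exits counted from Day 2: before Day 85 no scheduled ECG competes, so every ET ECG is kept. Share: 140/363 = 39%.

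**Sensitivity.**
- Weighting Days 86-364 by exp(-ht), with h = -ln(1 - D)/365 and yearly dropout D from 10% to 40%, gives 50.5% to 51.8%.
- Moving scheduled ECGs at random within the Protocol Appendix 2 visit windows (±3 days at Weeks 12 and 24, ±7 days at Weeks 36 and 52) gives 47.6%.
- If exits fall exactly on protocol visits after Week 12, the ET ECG is displaced at Weeks 16, 30 and 44 (Days 113, 211, 309) and kept at Weeks 20, 24, 36 and 52, which is 3 of 7 visits (43%). Days 211 and 309 are the last days of their windows, so a visit one day late would reverse the result there.

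**Unscheduled ECGs.** If the scheduled ECG is on the nominal day, an unscheduled ECG on any other day of that window is displaced. If the scheduled ECG is 3 days off, an unscheduled one survives only within about 3 days of nominal. The number of such ECGs is not given, so no count follows.

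**The case against.** The strongest reply is that the situations of most concern have other by-arm routes. Protocol 7.1.3 and 7.5 require an abnormal ECG associated with signs or symptoms to be recorded as an AE or SAE if it meets the definition. SAP 7.1.6.1 tabulates AEs by arm, including those leading to discontinuation of drug or study. SAP 7.1.7.1 tabulates positively adjudicated MACE by arm. This stands. A reader might infer that the displaced ECGs enter no table at all. The documents do not support that: it is the ECG category that is lost, and only from the ECG table. The reply does not cover an asymptomatic change, which need not be recorded as an AE. Nor does an AE term show the shift from the baseline category.

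Follow-up also helps in part. Early leavers are due a Post Treatment Week 4 ECG, and SAP 3.8.2 summarizes ECGs from + 8 to + 30 days. A lasting abnormality can be seen there. One that resolves off drug is not seen, and the visit window of ±7 days around day + 28 allows an ECG as late as + 35, which is listed only.

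It is also tempting to read the 50% as a property of this trial. It is not. Window limits set at midpoints give about one half under even exits by construction. The figure also requires the ET ECG to fall within 7 days of last dose, whereas subjects who stop drug are asked or encouraged to continue visits (Protocol 3.2, 3.5.2), so an ET visit can come much later and outside these windows.

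Likewise, a reader might infer that most symptom-prompted ECGs are lost. The window arithmetic makes displacement likely for an unscheduled ECG on a random day, but the protocol schedules no symptom-prompted ECGs and gives neither their number nor their timing.

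Finally, the table is descriptive, makes no claim to show worst values, and vital signs are summarized the same way (SAP 7.3). Protocol 1.4 reports no clinically relevant ECG effect in Phase 1 and 2. These points limit the weight of the finding but do not remove the gap.

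**Conclusion.** The point holds in a limited form. Under SAP 7.5.1, Table 3-2 and 3.8.3, some on-treatment ET and unscheduled ECGs enter no ECG table and appear only in the listing. Clinically significant changes that are asymptomatic or transient then have no assured by-arm summary, whereas laboratory abnormalities have one through the worst postbaseline grade.

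The size is illustrative: 50% of possible ET days over Days 86-364, 47% with scheduled ECGs 3 days off, and about 39% from Day 2. All three rest on evenly spread exits and an ET ECG within 7 days of last dose. No number of affected subjects can be derived. The by-visit table is not wrong for what it describes. Adding to it is a cheap improvement rather than the correction of an error.

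**What to change.** In SAP 7.5.1, add a shift table by treatment group from baseline to the worst postbaseline investigator ECG category, using every scheduled, unscheduled and ET ECG from first dose to last dose + 30 days. Keep the by-visit table as it is. The time limit matches the laboratory summaries in SAP 7.2, and every ECG in that period would then be considered by at least one ECG table.

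The cost is one sentence in the SAP and one extra table from data already collected. The downside is that subjects with more ECGs have more chances of a finding, as they already do in the worst-value laboratory summaries.

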## **7.6. Other Safety Measures**

A data listing will be provided for subjects who become pregnant during the study.

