1.4. Risk/Benefit Assessment for the Study

As of January 2016, Filgotinib has been administered to more than 150 healthy subjects as single doses ranging from 1 to 200 mg, and as multiple doses at 25 to 100 mg twice daily, and 200, 300, and 450 mg daily for 10 days. In addition, filgotinib has been administered to more than 1000 RA subjects and more than 150 subjects with Crohn's Disease at daily doses ranging from 50-200 mg. In general, filgotinib has been safe and well tolerated in all populations studied.

Nonclinical studies in rats and dogs identified the testes and lymphoid tissue as target organs for filgotinib in long term repeat-dose toxicity studies. In both species, histopathological changes in the testes included germ cell depletion and degeneration, with reduced sperm content and increased cell debris in the epididymis and reduction in fertility in rats. The dog was determined to be the most sensitive species. A dose of 200 mg/day of filgotinib results in an estimated mean clinical AUC of 2.80 $\mu\text{g}\cdot\text{h}/\text{mL}$, which represents an exposure margin of 2.3, 1.8, and 3.4-fold when considering the mean AUC in male dogs at the no-observed-effect-levels (NOELs) in the 26 week and 39 week chronic toxicity studies, and the 39 week targeted exposure toxicity study, respectively. Decreased lymphocytes observed in nonclinical studies have not been shown in clinical studies.

Filgotinib has shown an increased risk of embryofetal malformations at exposures similar to human doses; the use of highly effective contraception in the subject population will be implemented in the study to mitigate this risk.

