7.7.2. Instructions for Reporting Special Situations

7.7.2.1. Instructions for Reporting Pregnancies

The investigator should report pregnancies in female study subjects that are identified after initiation of study medication and throughout the study, including the post study drug follow-up period, to Gilead DSPH using the pregnancy report form within 24 hours of becoming aware of the pregnancy.

Refer to Section 7.3 and the eCRF completion guidelines for full instructions on the mechanism of pregnancy reporting.

The pregnancy itself is not considered an AE nor is an induced elective abortion to terminate a pregnancy without medical reasons.

Any premature termination of pregnancy (eg, a spontaneous abortion, an induced therapeutic abortion due to complications or other medical reasons) must be reported within 24 hours as an SAE. The underlying medical reason for this procedure should be recorded as the AE term.

A spontaneous abortion is always considered to be an SAE and will be reported as described in Sections 7.1.1 and 7.1.2. Furthermore, any SAE occurring as an adverse pregnancy outcome post study must be reported to Gilead DSPH

The subject should receive appropriate monitoring and care until the conclusion of the pregnancy. The outcome should be reported to Gilead DSPH using the pregnancy outcome report form. If the end of the pregnancy occurs after the study has been completed, the outcome should be reported directly to Gilead DSPH. Gilead DSPH contact information is as follows:

Email: PPD and Fax: PPD

Pregnancies of female partners of male study subjects exposed to study drugs must also be reported and relevant information should be submitted to Gilead DSPH using the pregnancy and pregnancy outcome forms within 24 hours. Monitoring of the subject should continue until the conclusion of the pregnancy. If the end of the pregnancy occurs after the study has been completed, the outcome should be reported directly to Gilead DSPH, fax number PPD or email PPD

Refer to Appendix 5 for Pregnancy Precautions, Definition for Female of Childbearing Potential, and Contraceptive Requirements.

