All female subjects must also agree to refrain from egg donation and in vitro fertilization during study participation and for at least 35 days after the last study drug dose.

3) Contraception for Male Subjects

It is theoretically possible that a relevant systemic concentration may be achieved in a female partner from exposure to the male subject's seminal fluid. Therefore, male subjects with female partners of childbearing potential must agree to use condoms during study participation and for 90 days after the last study drug dose. Female partners of male study subjects should consider using one of the above methods of contraception as well. Male subjects must also agree to refrain from sperm donation during treatment and until at least 90 days after the end of dosing.

4) Unacceptable Birth Control Methods

Birth control methods that are unacceptable include periodic abstinence (e.g, calendar, ovulation, symptothermal, post-ovulation methods), withdrawal (coitus interruptus), spermicides only, and lactational amenorrhea method (LAM). Female condom and male condom should not be used together.

5) Procedures to be Followed in the Event of Pregnancy

Subjects will be instructed to notify the investigator if they become pregnant at any time during the study, or if they become pregnant within 35 days of last study drug dose. Subjects who become pregnant or who suspect that they are pregnant during the study must report the information to the investigator and discontinue study drug immediately. Subjects whose partner has become pregnant or suspects she is pregnant during the study are to report the information to the investigator.

Instructions for reporting pregnancy, partner pregnancy, and pregnancy outcome are outlined in Section [7.7.2.1](#).

Pregnancy Testing

All females of childbearing potential will have urine pregnancy testing every 4 weeks during the dosing period through 35 days after their last dose of study drug. During the dosing period when study visits are every 6-8 weeks, the subject will be provided with home urine pregnancy tests, and will be contacted every 4 weeks to report results of the urine pregnancy tests. If a positive urine pregnancy test is reported, the subject will be asked to return to the clinic for a confirmatory serum pregnancy test.

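### The SAP's pregnancy listing leaves out partner pregnancies that the protocol collects, and Appendix 5 gives male subjects no post-dose reporting period to match its own 90-day precaution period

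*SAP*

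**What the plan says.** **Planned output.** SAP 7.6 is a single sentence: "A data listing will be provided for subjects who become pregnant during the study". It does not mention partners, a post-dose period or the fields to be listed.

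**Investigator's duty.** Protocol 7.7.2.1 covers partners: "Pregnancies of female partners of male study subjects exposed to study drugs must also be reported", "using the pregnancy and pregnancy outcome forms within 24 hours". Monitoring continues until the pregnancy concludes. On later outcomes it says: "If the end of the pregnancy occurs after the study has been completed, the outcome should be reported directly to Gilead DSPH". No end date is set for this duty.

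**Instruction to subjects.** Protocol Appendix 5 item 5 asks female subjects to report a pregnancy at any time in the study or within 35 days of the last dose. For male subjects it says: "Subjects whose partner has become pregnant or suspects she is pregnant during the study are to report the information to the investigator". No post-dose period is given.

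**Precaution period for men.** In Appendix 5 item 3, male subjects with partners of childbearing potential "must agree to use condoms during study participation and for 90 days after the last study drug dose". They must also "refrain from sperm donation during treatment and until at least 90 days after the end of dosing".

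**Reason for the precautions.** Protocol 1.4 states: "Filgotinib has shown an increased risk of embryofetal malformations at exposures similar to human doses". Appendix 5 attributes the finding to animal studies, speaks of a possibility in humans on non-clinical grounds, and calls exposure of a partner through seminal fluid theoretically possible.

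**The concern.** There are two separate gaps on a risk that the protocol itself singles out.

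The first is in reporting. The sponsor will hold partner pregnancy and outcome forms, but no SAP section gives them a place. Protocol 7.7.2.1 says that a pregnancy is not in itself an adverse event, so a continuing or normal partner pregnancy would not reach the adverse event listings either. SAP 7.1.4 reconciles the clinical and safety databases for SAEs only.

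The second is in collection. The investigator can report only what he or she learns. After the last visit, a male subject following Appendix 5 item 5 has not been asked to come forward, although item 3 still asks him to take precautions.

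At stake is whether the pregnancy information in the study report is complete. No endpoint, test or efficacy estimate is affected.

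**Working it through.** The plan states no figure for this point, so there is none to reproduce. The check sets the periods side by side and computes the part of the male precaution period that falls after the last contact.

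**Periods compared**

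| | Precaution period after last dose | Subject's reporting period after last dose (Appendix 5 item 5) | Planned listing (SAP 7.6) |
|---|---|---|---|
| Female subjects | 35 days | 35 days | Yes, during the study |
| Partners of male subjects | 90 days | None stated | None |

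**Inputs for the gap**

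- Male precaution period: 90 days (Appendix 5 item 3).
- Last scheduled contact: Post Treatment Week 4, that is 28 days after the last dose, with a visit window of ±7 days (Protocol 6.6 and Appendix 2), so day 21 to day 35.
- Assumption: for a given subject, the study ends at his last visit.

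**Formula:** days without contact = 90 − day of last contact; share = days without contact / 90.

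- Visit at day 28: 90 − 28 = 62 days; 62/90 = 68.9%.
- Visit at day 35: 90 − 35 = 55 days; 55/90 = 61.1%.
- Visit at day 21: 90 − 21 = 69 days; 69/90 = 76.7%.

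**Who these figures describe.** They hold for male subjects with no contact after Post Treatment Week 4 who do not enter the extension: completers who decline or do not qualify, and subjects who leave the study. They do not hold for subjects who stop drug but stay on visits:

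- Drug stopped at Week 24, visits to Week 52: 28 weeks × 7 = 196 days of contact, so all 90 days are covered.
- Drug stopped at Week 36: 16 × 7 = 112 days, again all covered.
- Drug stopped at Week 44: 8 × 7 = 56 days, leaving 90 − 56 = 34 days.

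Subjects who enter the extension have no Week 4 visit and pass to a study whose rules are not in these documents.

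**Female subjects, for comparison.** The same visit leaves 35 − 28 = 7 days (0 to 14 across the window), but those days carry a reporting instruction. The remaining question is whether the SAP listing, limited to the study period, is meant to include them.

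**The case against.** The strongest reply is that partner pregnancies are already reportable. That is correct. Protocol 7.7.2.1 makes reporting mandatory, within 24 hours, with outcomes and no end date. A reader might infer from SAP 7.6 and Appendix 5 that partner pregnancies go unreported; the documents do not support that. What they support is narrower: no planned output, and a weak route by which a late pregnancy would reach the investigator.

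A reader might also infer that all pregnancy outcomes are lost to the analysis. That does not hold either. Protocol 7.7.2.1 makes spontaneous abortion, and termination for medical reasons, an SAE; Protocol 7.1.2 does the same for a congenital anomaly. SAP 7.1.6.1 lists all SAEs, and SAP 7.1.4 reconciles them. Adverse outcomes in female subjects therefore have a place, and SAP 7.6 does not say that its listing omits outcome. The gap concerns partners, and pregnancies that are not themselves SAEs.

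It can be said that the end of the study is ambiguous. Protocol 3.6 defines it at study level, by the last subject, and on that reading early finishers would be covered for longer. But item 5 adds 35 days for female subjects, which suggests that its authors did not take the study period to reach that far after the last dose.

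Finally, consent pages are not in the material available, and a subject-facing instruction may stand there. So the claim is limited to Appendix 5.

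**Conclusion.** The point holds in two parts. SAP 7.6 provides no output for partner pregnancies that the protocol requires to be collected. Appendix 5 item 5 does not match item 3 or Protocol 7.7.2.1 on how long a male subject should report.

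For male subjects whose contact ends at Post Treatment Week 4 and who do not enter the extension, 62 of 90 days (69%; 61 to 77% across the visit window) have neither a scheduled contact nor a reporting instruction in Appendix 5. This assumes that the study ends for each subject at his last visit. The number of men affected cannot be derived, because the documents give neither the expected sex split nor the uptake of the extension.

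A reader might take this as a gap around an established human harm. The documents do not go that far: the evidence is non-clinical, partner exposure is called theoretical, and the 90 days are described as a condom and sperm-donation period, not as a period of established exposure. This is an inexpensive safety-reporting improvement that should be made. It does not threaten the trial's conclusions.

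**What to change.** **SAP 7.6.** Extend the listing to all pregnancies reported under Protocol 7.7.2.1, in subjects and in partners of male subjects. Show treatment group, last-dose date, timing relative to dosing, and outcome as known at data finalization. Reconcile it with the sponsor's safety database in the way SAP 7.1.4 already does for SAEs. Tying the listing to what is reported under 7.7.2.1, instead of to a fixed number of days, keeps it as wide as the investigator's duty.

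**Protocol Appendix 5.** Reconcile the partner-reporting period in item 5 with item 3 and with 7.7.2.1, and state what the end of the study means for an individual subject. No contraception or treatment rule needs to change for this.

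**Cost.** About one sentence in each document. The pregnancy forms, the outcome forms and the safety database already exist. The real cost is timing: outcomes of late pregnancies will arrive after database lock, so the listing needs a stated cut-off and a later update.
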